2.2. Safety Analysis for Safety Review Team (SRT) Meetings

Safety and tolerability monitoring are planned at the following trial milestones:

- After 50 new subjects are treated through Week 4 until all subjects in the trial (~135) have been treated through week 4, which will be 1st through 3rd SRT meeting or approximately quarterly, whichever comes first
- Approximately quarterly after all subjects have been treated through Week 4 through the end of the trial

The results of these analyses will determine if the trial will continue at the current dose levels. Trial blind will not be broken, and all analyses will be done with pooled treatment groups. The content of the outputs for the safety review meetings is described in the study Safety Review Meeting Charter.

2.3. Primary Analysis

The primary analysis will be conducted after all subjects have completed Core Phase or discontinued prematurely. The analysis includes all data collected at the time of database lock.

2.4. Final Analysis

The final analysis will be performed after all subjects have completed OLE Phase or discontinued prematurely. Full safety and efficacy data for subjects who entered OLE treatment period will be included.

2.5. Changes from the Protocol Planned Analyses

The definition of HZN-825 Baseline has been updated from the protocol. This adjustment is essential to facilitate a comprehensive comparison of data over 104 weeks across all cohorts. As a result, HZN-825 Baseline has been redefined as the latest measurement prior to the first dose of study drug (either HZN-825 or Placebo) during the Core Phase.

For efficacy analysis, the prior use of IPF approved therapy will be used as a covariate in the mixed model for repeated measures instead of concomitant use of IPF approved therapy. In earlier protocol versions, the prior use of IPF approved therapy was used as a stratification factor, while concomitant use of IPF approved therapy was restricted. In protocol version 4, concomitant use of IPF approved therapy was permitted and used as a stratification factor. However, only a small number of enrolled subjects were on concomitant IPF therapy. To ensure a robust model estimate, the prior use of IPF approved therapy will be used in the model. Additional subgroup analysis will be conducted as needed, focusing on subjects who were on concomitant use of IPF approved therapy.

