# 9.6.1.3 Primary Efficacy Endpoint Analysis

The estimand for the primary efficacy analyses will be constructed to compare the primary endpoint between each dose regimen of fipaxalparant (HZN-825) and placebo using the treatment policy strategy approach to intercurrent events. All subjects who are randomized and take at least 1 dose of trial drug will be included in the primary efficacy analyses (FAS).

The primary efficacy endpoint will be change from Baseline in FVC % predicted to Week 52. A mixed model for repeated measures (MMRM) analysis of covariance model will be fit to the data using observed change in FVC % predicted values from all planned post-Baseline assessments (i.e., Weeks 4, 16, 28, 40, and 52) with covariates of stratification factors (concomitant use of IPF therapy [yes, no] and FVC % predicted at Baseline [≥70%, <70%]), treatment group, visit and visit-by-treatment group interaction. The unstructured variance-covariance matrix will be used in the model. Treatment group least squares means, associated standard error (SE) and their differences (each fipaxalparant [HZN-825] group minus placebo separately), SE of the difference, 90% CIs and p-value overall and for each visit will be provided.

For subjects with missing data at 1 or more time points, the available data will be included in the analysis.

As a supplemental analysis to assess the robustness of the efficacy analysis results, the effect of each dose regimen of fipaxalparant (HZN-825) will be compared to placebo using the following measurements and methods:

Horizon Therapeutics Ireland DAC (a wholly owned subsidiary of Amgen Inc.) Date: 07 October 2024

IND 154671

Fipaxalparant (HZN-825) Protocol: HZNP-HZN-825-303 Version 5.0, Amendment 4

- Change in FVC (in mL) from Baseline to Week 52 using a similar MMRM analysis method as described for the primary efficacy endpoint
- Cumulative response curve comparison using the Kolmogorov-Smirnov test on:
  - The range of improvement (≥0% to ≥15% with a 5% increment) and worsening (< -15% to <0% with a 5% increment) based on the change in FVC % predicted value from Baseline at Week 52

  - The range cut-off values from less than -300 mL to greater 100 mL with a 100-mL increment based on the change in FVC (in mL) from Baseline at Week 52

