# 9.6.1.8 Interim Analysis

An interim analysis of the primary efficacy endpoint will be conducted using unblinded data after

This analysis will have 2 potential outcomes:

- If neither dose regimen of fipaxalparant (HZN-825) shows better efficacy compared to placebo with an acceptable safety profile, the trial will be discontinued for futility.
- If 1 or both dose regimens of fipaxalparant (HZN-825) show better efficacy compared to placebo with an acceptable safety profile, the trial will continue with no changes.

Fipaxalparant (HZN-825)

Version 5.0, Amendment 4

Protocol: HZNP-HZN-825-303

Fipaxalparant (HZN-825) Protocol: HZNP-HZN-825-303 Version 5.0, Amendment 4

The futility analysis will not be used to make a positive determination of efficacy to stop the trial.

Conditional power will be used to determine which of the options is chosen, with a conditional power of  $\geq 10\%$  required for at least 1 dose regimen to continue the trial. Other statistics, such as Bayesian statistics, may also be used for the futility analysis and dose selection.

To support the dose selection and as part of the Week 28 unblinded interim analysis, the FVC % predicted change from Baseline at Week 28 will be evaluated in subjects who were randomized with concomitant standard-of-care treatment at Baseline. Approximately 60 subjects in the standard-of-care stratum with 28 weeks of data (approximately 20 subjects per arm) will be included. The positive signal in the FVC % predicted change from Baseline at Week 28 and related results in standard-of-care subjects will support the dose selection and future trial design.

Additionally, safety will be assessed, and an fipaxalparant (HZN-825) dose regimen that has an unacceptable safety profile will be discontinued and subjects assigned to that dose regimen would be assigned to the other dose regimen for the remainder of the trial, if the other dose regimen continues.

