4. SUBJECT DISPOSITION

4.1. Subject Enrollment and Disposition

The number of subjects who are screened, randomized, and included in each analysis set will be presented. Patients who received study treatment, completed or discontinued from the study treatment will be presented based on the number of patients in each treatment group and overall for each study phase. Reasons for not completing the study or treatment will be summarized for each treatment group and for each study phase.

A summary of subject enrollment will be provided by treatment groups for individual investigators within each country, and overall based on the all subjects randomized set.

A similar enrollment table will be provided by randomization stratum based on the all subjects randomized set. The strata used for the randomization are as follows:

- Concomitant use of approved IPF therapy (yes vs no)
- FVC% predicted ($\geq 70 \text{ vs} < 70\%$)
- Prior use of approved IPF therapy (yes vs no)

The denominator for the percentage of subjects in the stratum will be the total number of randomized subjects in applicable treatment group and overall. If there are discrepancies in the value used for stratification assignment between the Interactive Response Technology (IRT) and the clinical database, the value collected in IRT will be used in efficacy analysis. A listing of subjects with discrepancies in the value used for stratification assignment between the IRT and the clinical database at the time of data finalization will be provided.

The randomization schedule used for the trial will be provided as an appendix to the CSR.

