6. EFFICACY ANALYSES

6.1. Core Phase

6.1.1. Primary Efficacy Endpoint

6.1.1.1. Primary Analysis Method

The primary efficacy endpoint is the change from Baseline in FVC % predicted at Week 52. The FVC% predicted data are collected at Screening, Day 1, Week 4, Week 16, Week 28, Week 40, and Week 52.

The estimand for the primary efficacy analyses is constructed to compare the primary endpoint between each dose regimen of HZN-825 and placebo, using the treatment policy strategy approach to ICEs without data imputation in FAS subjects.

The primary analysis will be based on a mixed model for repeated measures (MMRM) analysis of covariance (ANCOVA) model using observed change in FVC % predicted values from all planned post-baseline assessments (Weeks 4, 16, 28, 40 and 52) with covariates of treatment group (300 mg HZN-825 QD, 300 mg HZN-825 BID, placebo), prior use of IPF therapy [yes or no], FVC% predicted at baseline [≥ 70, <70], visit week, and treatment by visit week interaction. An unstructured covariance matrix will be used as the primary analysis method; if the model does not converge, the following three variance-covariance matrices or by visit week will be attempted in order until one converges: heterogeneous Toeplitz (TOEPH), heterogeneous compound symmetry (CSH), and Toeplitz (TOEP).

Treatment group least squares means, associated standard error (SE) and their differences (each HZN-825 group minus placebo separately), SE of the difference, 90% CIs and p-values for each visit will be provided with Week 52 estimands being the primary efficacy endpoint result. A line plot of the LS mean value for FVC% predicted change from Baseline will be plotted by treatment group for each visit week over time, including the estimated 90% CI around each LS mean.

Change in FVC % predicted will also be summarized descriptively for observed cases at each visit.

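### The primary MMRM leaves out continuous baseline FVC % predicted and concomitant IPF therapy for reasons that do not require it; adding both is a small, nearly free precision gain, and the prior-use coding and PFS strata need settling before unblinding

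*SAP*

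**What the plan says.** **Primary model.** SAP 6.1.1.1 fits treatment group (the two HZN-825 doses and "placebo), prior use of IPF therapy [yes or no], FVC% predicted at baseline", split at 70%), then "visit week, and treatment by visit week interaction". SAP 2.5 declares that "the prior use of IPF approved therapy will be used as a covariate in the mixed model for repeated measures instead of concomitant use" and explains it by saying that "only a small number of enrolled subjects were on concomitant IPF therapy". It gives no count. Protocol 9.6.1.3 describes the model "with covariates of stratification factors (concomitant use of IPF therapy [yes, no] and FVC % predicted at Baseline". Protocol v5.0 (07 October 2024) is later than SAP v2.0 (16 August 2024), which was written against protocol v4.0.

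**Continuous baseline.** It is in neither primary model. The protocol's summary of changes for v4.0 says it was removed because of collinearity with a stratification factor.

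**Randomisation factors.** SAP 4.1 and 5.2 list prior use, concomitant use and the FVC category. SAP 5.2 marks prior use as applying before v4.0. Where IRT and the clinical database disagree, SAP 4.1 says "the value collected in IRT will be used in efficacy analysis".

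**Other models.** The key secondary logistic model (SAP 6.1.2.1) includes the baseline value and stratifies by prior use and FVC category. The hospitalisation Cox model (6.1.2.6) stratifies by prior use, the PFS Cox model (6.1.2.7) by concomitant use. Protocol 9.6.1.4 gives both Cox models the same strata as the logistic model. The multiple imputation (SAP 6.1.1.3) uses baseline FVC % predicted and the randomisation factors, without naming them.

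**Definitions.** SAP 7.4.1 counts a medication as prior only if it ended before the first dose. Protocol 9.3.1.1 requires at least 3 months of stable background therapy before Day 1 for subjects taking it.

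**The concern.** The usual default is to adjust for the factors used in randomisation and for the baseline value of the outcome. The two reasons given for departing from it are weak. A yes/no covariate with few positives costs one degree of freedom and does not destabilise the treatment contrast. Collinearity between two baseline terms widens the standard errors of those two coefficients, not that of a randomised treatment difference. The SAP does not hold to the collinearity reason either, since its logistic model carries both the baseline value and the FVC category.

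Only treatment interacts with visit. The FVC category therefore enters as a constant shift and cannot follow a baseline effect on decline that grows over the year.

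The definition of prior use matters more for pre-specification. A subject on nintedanib or pirfenidone at Day 1 has used it for at least 3 months, yet is not a prior user under SAP 7.4.1. Two analysts could code that subject differently in the primary MMRM, the rank ANCOVA, the logistic model and the hospitalisation model.

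**Working it through.** **1. The plan's own figures.** Inputs (SAP 1.3): difference 3, SD 9, 45 per arm. SE = 9 × √(2/45) = 1.897. P(observed > 1 | true 3) = 85.4%, P(observed > 2 | true 3) = 70.1%, P(observed > 2 | true 0) = 14.6%. The plan states 85%, 70% and 15%, so these reproduce. At two-sided α = 0.10 (SAP 3.4), power for 3 points is Φ(3/1.897 − 1.645) = 47.5%.

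**2. Type I error.** Suppose a share p of subjects takes concomitant therapy and this shifts the outcome by e points (both assumed). Then R² = p(1−p)e²/81. If the factor is balanced by stratification but left out, the real level is 2[1 − Φ(1.645/√(1−R²))]. With p = 10% and e = 2 to 6, R² = 0.4% to 4.0% and the real level is 0.099 to 0.093. The omission makes the test slightly conservative.

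**3. Simulated MMRM.** REML, unstructured covariance, Weeks 4/16/28/40/52, 135 subjects, 4,000 trials per setting, true Week 52 difference 3 (BID vs placebo), Week 52 SD 9.

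Assumed, because the documents do not give them:
- SDs of 4.0, 5.5, 6.8 and 8.0 at the earlier visits, correlation 0.85^lag, 15% monotone dropout;
- baseline N(70, 13) truncated at 45;
- half the subjects randomised under each therapy factor, 45% prior and 10% concomitant users;
- the baseline-change correlation r, with the effect growing either with week or with the visit SD.

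| Setting | Power %, SAP model | + both as main effects | + concomitant use and baseline-by-visit | SE, last vs SAP |
|---|---|---|---|---|
| nothing prognostic | 45.4 | 45.2 | 45.2 | +0.2% |
| r = 0.1 | 45.2 | 45.1 | 45.6 | −0.3% |
| r = 0.2 (week) | 45.2 | 45.1 | 46.2 | −1.8% |
| r = 0.2 (SD) | 45.6 | 45.8 | 46.2 | −1.0% |
| r = 0.39 (week) | 45.3 | 45.0 | 50.1 | −7.9% |
| r = 0.39 (SD) | 47.2 | 48.4 | 50.1 | −4.7% |

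The Monte Carlo SE of a paired power difference is 0.15 to 0.48 points. Simulated type I error is 9.0% to 10.1% in the extended model and 7.6% to 10.1% in the SAP model (Monte Carlo SE 0.5 points).

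**4. Closed-form check.** Full adjustment shrinks the SE by 1 − √(1−r²): 0.5%, 2.0% and 7.9% at r = 0.1, 0.2 and 0.39. The week pattern gave 0.3%, 1.8% and 7.9%.

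**5. Concomitant use alone.** With a 4-point shift and 10% users, power runs 45.3 → 45.3 → 45.4 across the three models, so there is essentially no gain. A simpler Week 52 calculation without any prior-use term gives 47.4% → 48.0% for the same inputs.

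**6. Collinearity.** For a normal baseline with 50% to 70% of subjects at or above the cut, the variance inflation factor of the two baseline terms is 2.4 to 2.75. In a Week 52 ANCOVA with nothing prognostic, the treatment SE moved only from 1.90 to 1.91.

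**7. Coding and strata.** If 5% to 10% of 135 subjects are on therapy at Day 1 (assumed), 7 to 14 subjects have an open prior-use code. At 10%, the PFS model has 13.5/(2 FVC strata × 3 arms), or about 2.3 concomitant users per cell. The SAP judged the factor too sparse for a covariate, yet stratifies on it here.

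**The case against.** The strongest reply is that these are declared choices. SAP 2.5 names the swap, its history and its reason, and fixes one model. Protocol and SAP agree on leaving out continuous baseline, and the 70% category already takes up part of the severity effect. The material gain needs a baseline-by-visit term that neither document planned and a correlation that neither gives. The logistic model is a doubtful precedent, because protocol 9.6.1.4 does not include the baseline value and SAP 2.5 does not declare that addition. PFS p-values are not used for inference (SAP 3.4). All of this stands and keeps the point small. It does not supply a reason for the omissions, and it does not settle the coding of ongoing users.

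A reader might also infer more than the documents support:

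- **That the small number of users contradicts the protocol.** Protocol 9.6.1.8 says "Approximately 60 subjects in the standard-of-care stratum with 28 weeks of data (approximately 20 subjects per arm) will be included", but that is a plan carried over from v4.0. SAP 2.5 reports what was enrolled, and SAP 2.1 makes the Week 28 evaluation optional without a number. A missed target is not a contradiction.
- **That SAP 3.3 would cancel the concomitant-use subgroup analysis.** That depends on the users being at most 10% of treated subjects, and no count is given.
- **That the primary test is invalid.** Step 2 and the simulation show no inflation.

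**Conclusion.** The point holds as a modest improvement in precision and pre-specification. Neither stated reason requires leaving out continuous baseline FVC or concomitant use. The expected gain is about 0 to 1 power point at r = 0.1 to 0.2, and about 3 to 5 points (2.9 to 4.8) only at r = 0.39. As main effects alone the two terms change power by −0.3 to +1.2 points, so most of any gain comes from baseline-by-visit. Concomitant use belongs in the model because it was a randomisation factor and costs one degree of freedom, not because it sharpens the estimate.

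These sizes rest on assumed correlations, visit SDs, dropout and therapy shares. The two wording gaps do not depend on any of those assumptions. They are the undefined prior-use code for ongoing users and the unexplained difference in Cox strata, which departs from protocol 9.6.1.4.

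**What to change.** Amend the SAP, by blinded staff, before Core Phase unblinding.

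1. **SAP 6.1.1.1.** Keep prior use and the FVC category. Add continuous baseline FVC % predicted with baseline-by-visit, and concomitant use (yes/no). Keep the existing covariance sequence as the only response to non-convergence.
2. **Prior use.** State how the covariate is coded for subjects on therapy at Day 1, for example any nintedanib or pirfenidone before Day 1, including ongoing use. Say that this is separate from the medication definition in SAP 7.4.1. Name the data source for subjects randomised under v4.0 or later, because the IRT rule does not establish that a prior-use value exists for them. In SAP 6.1.1.3, name the factors in the imputation model in the same terms.
3. **SAP 6.1.2.7.** Stratify PFS by prior use, as in 6.1.2.6 and the logistic model. Add no further strata to the logistic or Cox models.
4. **SAP 2.5.** Record these changes, the move of the logistic and Cox models to prior use, and the baseline term already in the logistic model.

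Cost: SAP wording, no new data and no protocol amendment. The model uses 6 more degrees of freedom (1 concomitant use, 1 baseline, 4 baseline-by-visit), with an SE about 0.2% larger if none of the terms is prognostic.

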3. GENERAL CONSIDERATIONS FOR DATA ANALYSES

Categorical variables will have the number and percentage of subjects in each category presented; for continuous variables, the number of subjects (n), mean, standard deviation (SD) or standard error (SE), median, first quartile (Q1), third quartile (Q3), minimum, and maximum will be presented.

All statistical tests will be 2-sided and performed at the 10% significance level unless otherwise specified.

For additional details on data presentation, refer to the tables, listings, and figures (TLF) document.

3.1. Analysis Sets

Analysis sets define the subjects to be included in an analysis. Analysis sets and their definitions are provided in this section. Subjects included in each analysis set will be determined before the trial blind is broken for analysis.

For each analysis set, the number and percentage of subjects eligible for inclusion, as well as the number and percentage of subjects who were excluded and the reasons for their exclusion, will be summarized by treatment group.

A listing of reasons for exclusion from analysis sets will be provided by subject.

3.1.1. All Subjects Randomized Set

All Subjects Randomized Analysis Set includes all subjects who were randomized in the trial. This analysis set will be used for disposition summaries and will be analyzed by randomized treatment group.

3.1.2. Full Analysis Set

The Full Analysis Set (FAS) includes all subjects who were randomized and took at least 1 dose of study drug. This is the primary analysis set for efficacy analyses for the Core Phase. Subjects will be analyzed by randomized treatment group.

3.1.3. Safety Analysis Set

The Safety Analysis Set for the Core Phase (SAF) includes all subjects who took any dose of study drug during the Core Phase. This will be the primary analysis set for Core Phase safety analysis. Subjects will be analyzed by actual treatment received.

3.1.4. OLE Phase Analysis Set

The OLE Phase Analysis Set (OLE-SAF) includes all subjects that are enrolled in OLE Phase and took at least 1 dose of study drug during the OLE Phase. This analysis set will be the

Version 2.0

primary analysis set for both efficacy and safety for the OLE Phase and combined periods. Subjects will be analyzed by actual treatment received in Core Phase.

3.1.5. Pharmacokinetic Analysis Set

The Pharmacokinetic (PK) Analysis Set will include all randomized subjects who took at least 1 dose of study drug and have at least 1 nonmissing postdose concentration value reported by the PK laboratory. This is the primary analysis set for all PK analyses.

3.2. Subject Grouping

For analyses based on the FAS Analysis Set, subjects will be grouped according to the treatment to which they were randomized. For analyses based on the Safety Analysis Set, subjects will be grouped according to the actual treatment received. Actual treatment will be classified as follows:

- A subject who received only placebo will be classified as a subject in the placebo group.
- A subject who received any active treatment will be classified as a subject in the active treatment group.
- A subject who received different active doses at different dosing visits during the study will be included in the group of the highest active dose that he/she received.

For the PK Analysis Set, subjects will be grouped according to the actual treatment they received.

3.3. Examination of Subject Subgroups

Subgroupings based on the baseline characteristics listed below may be explored for analysis of the primary efficacy endpoint and key secondary efficacy endpoint.

The presumed prognostic baseline characteristics include the following:

- 1. Age (< 65 years and ≥ 65 years)
- 2. Sex (male and female)
- 3. Weight (<65 kg and $\ge65 \text{ kg}$)
- 4. Race (American Indian or Alaska Native, Asian, Black/African American, Native Hawaiian or Other Pacific Islander, White, or Other)
- 5. Baseline FVC% predicted (\geq 70%, <70%)
- 6. Concomitant use of approved IPF therapy (i.e., nintedanib or pirfenidone): yes or no

Version 2.0

- 7. Prior use of approved IPF therapy (i.e, nintedanib or pirfenidone): yes or no
- 8. IPF diagnosis duration ($< 3 \text{ years}, \ge 3 \text{ years}$)
- 9. Region (North America, Europe, South America, Africa, Asia (including Japan) and Australia)

If the actual size of the individual subgroup category is too small (\leq 10% of treated subjects), then the individual groups will be pooled in a meaningful way. If pooling cannot be done (e.g. if there are only two categories in the subgroup) then the subgroup analysis will not be performed.

